1.0 PROTOCOL SUMMARY AND/OR SCHEMA

Understanding how people make decisions about ultraviolet radiation (UVR) protection is critical to the development of melanoma risk reduction interventions, since UVR exposure is the primary modifiable risk factor for melanoma. Strategies available for UVR protection include consistent sun avoidance and shade-seeking, as well as use of sunscreen, clothing, and hats. However, individuals at high risk for melanoma, including first-degree biological relatives (siblings, children, or parents) are inconsistent in their UVR protection behaviors [22-24]. This behavioral inconsistency is significant for health outcomes since even a few episodes of sunburn can greatly increase skin cancer risk. Understanding the decisions that govern variations in UVR protection would greatly improve our ability to influence these behaviors. While extensive prior research has examined the role of individual differences (such as intentions, beliefs, and demographic differences) in average levels of UVR protection, this study will focus on developing a measurement strategy to capture within-person variability, or level of consistency, in UVR protection.

To understand UVR protection decision-making, we will use a mixed qualitative and quantitative approach dictated by ethnographic decision tree modeling (EDTM; [1, 2]). This mixed model approach is a well-established approach to elucidating the process of decision-making by identifying factors that groups of people use to make real-life decisions that has been used in anthropology, sociology, and psychology for 25 years. The central goal of EDTM is to uncover and validate the criteria that influence decision making about a particular task. EDTM is distinct from other mixed model designs because EDTM addresses cognition around decision making in particular, making it highly relevant to our study goals.

Using EDTM guidelines (described in greater detail on page 7), we will develop and establish the validity of decision models to explain daily decision-making about sunscreen use, shade-seeking, and UVR protective clothing use in melanoma first-degree relatives (FDRs). This study will involve two phases. In Phase I, we will conduct qualitative ethnographic interviews with 25 melanoma FDRs and generate a decision model for each UVR protection outcome for each melanoma FDR and then will construct a composite decision-making model incorporating findings across all 25 interviews for each of the three UVR protection outcomes (i.e., sunscreen use, shade-seeking, and UVR protective clothing use). Following this, in Phase II, we will establish the validity of the models using ecological momentary assessment of UVR protection (over 14 summer days, at 1 pm and 5 pm daily) in 60 different FDRs of 60 different melanoma patients. We will report on the level of success of the decision-making models in predicting behavioral performance. We will also examine the influence of between- and within-person changes in melanoma threat and efficacy, drawn from Witte's Extended Parallel Processing Model [3], as well as satisfaction with UVR protection maintenance, drawn from Rothman's theory of health behavior maintenance [4-6] on the three major outcomes of the study (i.e., sunscreen use, shade-seeking, and UVR protective clothing use). We will recruit equal numbers of women and men, and of those who perceive high and low advantages of tanning, to both phases of the study. The study will increase our understanding of the decision-making context of behavioral maintenance of UVR protection, and dictate strategies to reduce behavioral inconsistency - and increasing maintenance - of UVR protection in those at risk for melanoma and the general population.

2.0 OBJECTIVES AND SCIENTIFIC AIMS

Specific Aim I (*Phase I*): To generate models explaining decision-making about four UVR protection behaviors (sunscreen use, shade-seeking, hat use, use of protective clothing) in melanoma FDRs.

Specific Aim II (*Phase II*): To examine theory-driven affective and cognitive predictors of UVR protection maintenance (sunscreen use, shade-seeking, hat use, and use of UVR protective clothing) assessed in real time.

3.0 BACKGROUND AND RATIONALE

Understanding behavioral patterns in UVR protection is critical to melanoma risk reduction. Melanoma accounts for about 70% of skin cancer deaths each year, making it the most fatal form of skin cancer [7]. Fortunately, risk factors for melanoma are relatively well-understood, as UVR delivered via sunlight is the predominant modifiable cause of melanoma, with approximately 65% to 90% of melanomas caused by UVR [8-11]. Accordingly, melanoma prevention recommendations inc Jude daily sun protection strategies such as sun avoidance in the middle of the day when UVR exposure is the highest, use of hats and clothing to block UVR exposure, and sunscreen use on exposed body parts [7, 12]. These recommendations are relevant to the general population, but even more important for those at high risk by virtue of their family history, a sun-sensitive phenotype (light skin and eyes, red hair) or other risk factors such as dysplastic nevus syndrome (the presence of many moles with irregular borders or coloring; [13]). Over and above cumulative UVR exposure, diverse *patterns* of UVR exposure, variations in the consistency with which some people engage in UVR exposure behaviors, lead to different levels of risk, which highlights the need to understand protection patterns with detail and nuance. For example, intermittent or recreational sun exposure, particularly beach and waterside activities, appear to increase risk much more than occupational exposure. Even in the context of regular sun protection a few UVR exposure episodes substantially increase risk [14-16].

UVR protection is inconsistently practiced among individuals at risk for melanoma. In national studies of UVR protection behavior, including the National Health Interview Survey [17] and the Behavioral Risk Factor Surveillance System [18], UVR protection is recalled cumulatively over large periods of time such as a year, with global indicators of usual behavior (such as "sometimes" or, "most of the time") used to indicate different types of UVR protection. This is also true for intervention studies, where cumulative, global self-report strategies are used to indicate intervention outcomes [19]. Direct measures of UVR protection have also been used less-widely and include redemption of a sunscreen coupon on the beach [20], and direct visual inspection of the skin [19, 21]. Using the predominant, global retrospective measurement strategy, inconsistent UVR protection is the *norm* for individuals with a family history of melanoma [22-26]. For instance, Azzarella and colleagues [22] found that 47% of first-degree relatives of melanoma patients used sunscreen on their face inconsistently and 71% sought shade inconsistently (e.g.,

rarely, sometimes, often, more than half the time). Geller and colleagues [23] found that 46% of siblings of melanoma patients did not regularly use sunscreen. In a trial to improve early detection and prevention behaviors in melanoma siblings that included telephone motivational interviewing and tailored educational materials, 30% of siblings in control and treatment groups used sunscreen sporadically or not at all [24].

Decision-making has a potentially important role in cancer prevention behaviors, but has not been studied. Medical decision-making research has paved the way to an improved understanding about how people choose the best course of cancer screening, or cancer treatment [40, 41]. Useful decision aids have been developed to facilitate patients' deliberate analysis of the benefits and drawbacks of alternative medical courses of action that maximize satisfaction and minimize regret [42]. In contrast, research in decision-making about cancer prevention "is in its infancy" [43]. The emerging paradigm of naturalistic decision-making proposes that health-related decisions made outside the clinic setting, in naturalistic environments, necessarily entail evaluation of the ecological context where the decision is made [44]. In the context of cancer prevention, naturalistic decision-making may be quite important in the repeated assessment of a single behavioral option - such as whether to use sunscreen.

Daily assessment could also enhance understanding of the decision-making context for UVR protection. There is a substantial literature examining predictors of UVR protection (including seeking shade, sunscreen use, wearing sun protection hats and clothing) in those at increased risk for melanoma, all have examined between-subject factors. For example, increased use of UVR protection has been reported among women, younger individuals [26], those with higher education [22], and those without a prior recent history of tanning [23]. Attitudinal factors related to increased use of protection include higher risk perception for melanoma [38], optimism [39], self-efficacy for UVR protection [22, 25], and the perception of fewer sunbathing advantages, social norms about UVR protection, and higher benefits and reduced barriers for sunscreen use [25].

Yet given the inconsistency with which UVR behaviors are performed, there are likely important decision-making factors that vary within-person as well as between-person, that help dictate social environmental and contextual variation in people's lives. Indeed, UVR protection utilized on family beach vacations may be different from what is utilized at soccer games or while walking a dog, and may differ based on the temperature, cloud cover, how rushed one feels in the morning, or might be based on the availability of clothing or sunscreen at any point in time. Understanding the basis of this variation may be useful in targeting interventions to encourage greater maintenance of UVR protection behaviors.

Ecological momentary assessment diary methods could capture information about daily patterns of UVR protection. Diary methods, in which research participants answer questions regarding their behavior or attitudes on their own without researcher involvement in real-time fashion, have been used extensively in sociological research to provide self-revealing records about day to day particulars of a person's life [27]. Qualitative and quantitative diaries are ecologically valid alternatives to global self-report questionnaires, as assessment points occur close to the time of the actual experience in the natural environment where it occurs. Paper and pencil diary methods have been used to examine UVR protection with general and high-risk populations [28-32], outdoor workers [33], and schoolchildren [34]. Diary methods have been validated against direct researcher observation [34] (in which the researcher is present with the participant and directly observes participant behavior), biological markers of sunscreen usage and UVR exposure [31], and questionnaires [30]. In individuals at high risk for melanoma, Brandenburg and colleagues [28, 29] showed that diary methods showed less underreporting of sunbathing occasions and sunburns.

Over the past decade, the use of computerized diaries to collect data in real time has supplanted paper and pencil methods as the gold standard for diary methodology. This is due to documented problems with paper and pencil methods - including the risk of participants' reporting on their behaviors cumulatively rather than in real time, or at the end of the reporting period. Additionally, ecological momentary assessment (EMA) minimizes missing data by providing automatic skip-outs and audible prompts, and allows for accurate reporting of missing data by reporting time of completion [35]. Adherence with these EMA methods is quite good, and appear to be highly dependent on training provided to participants (See Section 4.2 Intervention for the extensive training we provide to participants). In populations such as smokers, cancer patients, and pain patients using EMAs from three weeks to three months, adherence with "responding to auditory alerts," the most global measure of adherence, is in the range of 88-98% [35, 36].

In the current proposal given our short assessment time frame (14 days), the fact that we are examining an asymptomatic, non-clinical population, and the extensive training regarding how to use the interactive voice response (IVR) system that we offer, we believe that the study will be quite feasible with relatively low levels of nonresponse to audible prompts, and low levels of missing data overall. To achieve the high rates of adherence reported in the literature, we will follow the seven recommendations proposed by experts in the field of ecological momentary assessment [37]: 1) Integrate compliance concerns throughout the study protocol and build in compliance feedback and prompts for participants; 2) adequate training of subjects on the IVR; 3) make the IVR user-friendly; 4) program reminders into the IVR; 5) efficient handling within the IVR of question branching to administer correct questions in correct order; 6) built-in "livability" features to ease incorporation of IVR into their daily lives, and; 7) emphasize participant accountability for the data through tracking of adherence. We will evaluate reasons for refusal and patterns of missing data in primary statistical analyses. [name], an originator of EMA strategies and expert in methodological issues with EMA, has agreed to be a consultant on our study and will provide input during the EMA questionnaire development, implementation of the Phase II study, and data analysis.

In addition to our use of the IVR data, we will also use audio narrative diaries to explore how first-degree relatives of melanoma patients make decisions regarding sun protection on a daily basis. Audio diaries are research participants' verbal narratives about behavior, attitudes, or beliefs (dictated by a study's research focus) that are captured when participants speak into a recording device. The sun protection questionnaire delivered through the IVR system will include a statement at the end that will instruct participants to verbally record their own narrative of their sun protection use for the assessed time-period (i.e., either from morning to approximately 12:30 pm, or from approximately 12:30 to approximately 5 pm). Participants will be able to speak directly into their phones to record their audio narratives. The voice direction delivered through the phone will instruct participants to share in their own words the methods of sun protection they used for the assessed time-period and to explain the reasons why they chose to use such methods.

Ethnographic decision-tree modeling (EDTM) is an ideal method to examine decision-making about UVR protection. EDTM is a mixed (qualitative and quantitative) research method specifically designed to elucidate the process of decision-making by identifying factors that groups of people use to make real-life decisions. For the past 25 years, EDTM has been used by anthropologists and psychologists to model decisions such as medical treatment decision-making [45, 46], including needle sharing decisions among drug users [47] and the decision to recycle beverage cans [48]. In her comprehensive book on this method, Gladwin [2] outlined the theory behind EDTM, that decision-making involves a serial consideration of options that maximize outcomes subject to constraints dictated by simplifying rules or heuristics in making everyday decisions [49], and reducing the cognitive demand of decisions.

In practice, EDTM guides development and validation of a formal decision tree of choice for a specific decision task. The decision tree is comprised of an ordered set of "if then" decision rules that describe the principal considerations people use in making a choice for the decision task.

EDTM involves two phases. The goal of the first phase is to develop a composite decision model for a specific decision task. This phase involves ethnographic interviews with individuals comprised of open-ended questions to understand the factors that influence their decision-making for that decision task. After each ethnographic interview the researcher develops a decision tree for that research participant. When all interviews have been conducted, the researcher constructs a composite decision model for the decision task by grouping decision criteria used by the sample interviewed, and mapping their relationships in hierarchical order so that the flow of the 'if then' decision rules are predictive of choices in the sample. Reasons for performing the task come first in the hierarchical flow, with constraints for not performing the task coming second. Phase two involves model validation of the composite decision models generated in phase one. The composite model is tested using a new participant sample using a self-report survey that is based on the model; each question in the survey represents a criterion or decision factor. The goal of this phase is to quantitatively determine the sensitivity and specificity of the model.

Limitations of EDTM include the lengthy nature of the process and reliance on retrospective memory in model development. Strengths of the method involve the opportunity to develop a complex understanding of real-life decision making in a group of people, the sequential design that results in a quantitatively validated model of the decision-making context in question, and the ability of the model to explain when behavior is performed and avoided. EDTM is ideally situated to address applied research problems by pinpointing opportunities for intervention in real-world decisions in public health.

Health behavior theory may improve our understanding of the consistency of UVR protection. Witte's Extended Parallel Process Model [3] offers an account of the conditions under which illness threat may lead to health protective behavior. In the context of heightened illness threat (severity and susceptibility beliefs) and heightened beliefs that they can overcome the threat (self-efficacy and response-efficacy), people will act to do so via health protective behavior, or "danger control." In situations where threat is high but people don't believe they can manage it, behavioral avoidance, or "fear control" will result as people work to reduce their feelings of threat rather than their chances of becoming ill. Beliefs related to threat control include self-efficacy, or confidence that one can perform the behavior, and response-efficacy, or confidence that performing the behavior will protect against the health threat. Meta-analytic work examining this premise has found that pairing strong threat with high-self efficacy indeed maximizes behavior change [3]. In one of the only theories specifically addressing health behavior change maintenance, Rothman [50] has proposed and confirmed that satisfaction with the results of behavioral adoption - such as satisfaction with the results of smoking cessation or weight loss - determines whether individuals maintain health behavior over time [4, 5, 51].

We will examine these theory-based predictors - melanoma threat and efficacy, and satisfaction with UVR protection behavior - as between-subject and within-subject variables in this study. Accordingly, along with the most important decision factors, we will determine whether overall levels of these cognitive beliefs, or daily variations in these beliefs, are important in the maintenance of UVR protection over time in melanoma FDRs.

Study Significance. This is a measurement study aimed at understanding the discrete decision-making factors that dictate sun protection behavior on a daily basis. Given the clinical significance of even very few sunburn events, and the documented higher risk associated with some sun exposure contexts

(recreational) over others (occupational), new measurement strategies are needed in order to capture daily variation in sun protection, as well as the decision-making factors that dictate them. Accordingly, this new measurement strategy will be useful in assessing the impact of future intervention strategies that aim to increase the consistency of sun protection in higher and average risk individuals, and to address decision making factors that may set the stage for risky sun protection events.

An understanding of real time decision-making for UVR protection will provide a critical starting point to address the inconsistency with which those at high risk for melanoma practice this important cancer prevention behavior. Assessment of variations in daily decision-making about UVR protection will increase our understanding of the social and environmental context of behavioral maintenance of UVR protection, and will advance the development of novel interventions to reduce inconsistency in UVR protection in those at high risk for melanoma that can result in risky sunburns and intermittent high-doses of UVR. Decision-making models in cancer have been developed to address cancer treatment and screening decision-making; in contrast, research in decision-making about cancer prevention "is in its infancy" [43]. The study represents a novel first step in examining decision-making in cancer prevention, engaging with the complexities of measuring health decision-making in naturalistic settings where most health behaviors are performed [44]. The study also contributes to theoretical understandings concerning the processes by which health behaviors are maintained, or habituated, over time [50].

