4.0 OVERVIEW OF STUDY DESIGN/INTERVENTION

4.1 Design

Overview Guided by EDTM, we will first build models of decision-making about UVR protection using in-home ethnographic interviews with 25 melanoma FDRs (Phase I). We have chosen to interview 25 participants based on EDTM recommendations [1, 2]. We will build individual decision models for each UVR protection outcome for each melanoma FDR, and subsequently generate and composite decision models for the three primary outcomes (i.e., sunscreen use, shade-seeking, and UVR protective clothing use) representing the decision-making process and factors across the 25 melanoma FDRs interviewed. In Phase II, we will test the validity of each composite model. This will be completed using EMA data collection with 60 different melanoma FDRs who will report on their sunscreen use, hat use, shade-seeking, and use of UVR protective clothing and decision-making regarding these outcomes via an Interactive Voice Response (IVR) system (described below) and audio narrative diaries. We will examine the validity of each model and examine the influence of theory-driven affective and cognitive predictors of UVR protection maintenance across time.

Although there are wide variations in sun protection recommendations worldwide, we will follow the guidelines provided by the American Cancer Society. Their recommendations include: 1) limit direct sun exposure between the hours of 10 am and 4 pm; 2) if shade-seeking is not possible wear sun-protective clothing and hats, use sunscreen with an SPF of 15 or higher, and wear sunglasses that block UV rays when out in the sun.

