In generating the Phase 2 IVR assessment survey, we have translated each decision criterion identified in the four sun protection decision tree composite models generated in Phase 1 into a closed-ended question presented in yes/no format, so as to elicit from Phase 2 participants whether each decision criterion influenced their sun protection decisions during the assessed time period. For example, in our shade-seeking composite model we found that proximity to shade is a key factor dictating use of shade structures during outdoor activities. Accordingly, we developed a corresponding question "Was shade conveniently available? (yes/no)" and included this question on the IVR assessment survey to test the importance of this factor in the use of shade-seeking as a sun protection strategy. We have strived to phrase the closed-ended questions with key words and concepts identified in the decision criteria in the composite models [90].

During phase 2 recruitment, the study staff will record a series of choices (1st 2nd) of the 60 participants concerning when, during spring/summer months of 2012 and 2013, they will be available for the 14-day assessment period and they will be in the continental United States. Eligible participants will be consented (in clinic or verbally over the phone) within a week of their 14-day assessment period. Once consented, the study staff will administer a short demographic questionnaire, provide training on the participant's data collection responsibilities during the 14-day period that includes what to expect, how to respond to the IVR, and answer any questions that they may have.

IVR and audio diary training. Each training session will last approximately 15 minutes and will be done over phone by the study staff. The purpose of the training session will be to orient and prepare participants

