9.0 PRIMARY OUTCOMES

The following ultraviolet radiation protection (UVR) behaviors will be assessed as primary outcomes:

- Continuous sun avoidance and/or shade-seeking behavior
- Sunscreen use
- Use of UVR protective clothing
- Use of hats

Our first aim is to generate models explaining decision-making about three UVR protection behaviors (sunscreen use, shade-seeking, use of protective clothing) in melanoma FDRs. We will model daily decision-making processes for UVR protection through qualitative and quantitative research strategies. In Phase I, we will conduct in-home ethnographic interviews with 25 melanoma FDRs and generate a decision making model for each UVR protection behavior for each melanoma FDR, and subsequently construct a composite decision-making model for each of the UVR protection outcomes (i.e., sunscreen use, shade-seeking, and UVR protective clothing use) representing prominent decision making factors across all 25 FDRs interviewed. In Phase II we will establish the validity of the models via examination of daily decision-making about UVR protection using ecological momentary assessment via IVR (over 14 days in the summer/early fall, at approximately 12:30 pm and 5 pm daily) in 60 different melanoma FDRs from Phase I. As outlined in EDTM methodology, we will report on the level of success of the decision-making model in predicting uptake of each of the three UVR protection strategies.

Our second aim is to examine theory-driven affective and cognitive predictors of UVR protection maintenance (sunscreen use, shade-seeking, hat use, and use of UVR protective clothing) assessed in real time. We will examine the role of melanoma threat and efficacy beliefs in determining UVR protection maintenance drawn from Witte's Extended Parallel Processing Model [3], and will examine the role of satisfaction in UVR protection maintenance drawn from Rothman's theory of health behavior maintenance

[4-6]. We will examine both between-person and within-person changes in these predictors, as well as salient decision-making factors (Identified in Aim I), in predicting maintenance of sunscreen use, shade-seeking, hat use, and use of UVR protective clothing.

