11.0 BIOSTATISTICS

Overview. This exploratory study is divided into two phases. Phase I involves in-home interviews of 25 participants to understand the factors that affect participants' decision-making about UVR protection (sunscreen use, shade-seeking, use of protective clothing). Qualitative data analyses will be carried out in Phase I to generate an Ethnographic Decision-Tree Modeling (EDTM) tree as described in Section 4.2. For example, a participant may be most likely to use sunscreen when it is a sunny day and when he/she is outdoors, at the beach, or at an outdoor sporting event. The participant may also state that he/she uses sunscreen whenever together with a young child, even though it may not be a sunny day.

In Phase II, we plan to recruit a sample of 60 melanoma first degree relatives (FDRs) and use IVR technology so that they can record their daily sun protection behaviors and decision criteria. The IVR system will call participants twice daily at approximately 12:30 pm and 5 pm for a period of 14 days. The participant will use their telephone keypad to answer a series of questions on their UVR protection behaviors, which will be four dichotomous, self-reported outcomes: sunscreen use, shade-seeking, hat use, and protective clothing use). The assessment will also address factors that affect UVR protection behaviors. These decision factors are based on the qualitative data we collected in Phase I. For example, we will ask participants to report the presence or absence of environmental factors (e.g., weather conditions), convenience/situational factors (e.g., availability of sun protection items), and social-interpersonal (e.g., activities engaged in). Data collected through IVR will generally be analyzed by Generalized Estimating Equations (GEEs) to explore the decision factors that promote or hinder the probability of UVR protection behavior.

Specific Aim I: To generate models explaining decision-making about three UVR protection behaviors (sunscreen use, shade-seeking, use of protective clothing) in melanoma FDRs.

Aim I will involve the EDTM methodology described in Section 4.2. Audio-recorded narrative data will be coded and summarized into an EDTM tree.

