For example, decision factors such as convenience, weather, or social support for UVR protection may emerge as important factors. Because we are examining behaviors that involve highly complex interactions, we need to first understand the phenomenon more fully. Pertinent to Aim 1 is the use of descriptive statistics to summarize the sizes of the terminal decision nodes. Each node on the EDTM tree represents the pathway by which a person makes the decision to use or not to use UVR protection. The size of a terminal node in the EDTM tree represents the number of people who follow a specific decision

pathway. For example, we may find that many people do not use sunscreen if they do not find it before they leave home. In this hypothetical example, the decision factor of convenience trumps all other decision factors. We may therefore infer from the sizes of the nodes the importance of the corresponding decision pathways and specific decision splits. The most important advantage is that we will be better able to distinguish the factors that contribute to sunscreen nonuse from sunscreen use in order to separate the barriers from the facilitating decision factors.

Specific Aim II: To examine theory-driven affective and cognitive predictors of UVR protection maintenance (sunscreen use, shade-seeking, hat use, and use of UVR protective clothing) assessed in real time.

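### Section 11.0 contains no analysis that tests the composite decision trees, although the protocol promises that Phase II will validate them

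*Combined protocol and SAP*

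**What the plan says.** The commitment to validate appears three times. Section 4.1: "In Phase II, we will test the validity of each composite model". Section 1.0: "We will report on the level of success of the decision-making models in predicting behavioral performance". Section 9.0, under the first aim and with reference to EDTM methodology: "we will report on the level of success of the decision-making model in predicting uptake of each of the three UVR protection strategies". Section 3.0, in its general account of EDTM, says what the second phase is for: "The goal of this phase is to quantitatively determine the sensitivity and specificity of the model".

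Section 11.0 gives Aim I the coding of narratives into a tree, and then: "Pertinent to Aim 1 is the use of descriptive statistics to summarize the sizes of the terminal decision nodes". It adds: "We may therefore infer from the sizes of the nodes the importance of the corresponding decision pathways". For Phase II it says: "Data collected through IVR will generally be analyzed by Generalized Estimating Equations (GEEs) to explore the decision factors". Under Aim II, the worked GEE relates sunscreen use to one weather indicator, the step is repeated for other factors, and the number of covariates is left open. The only power or precision figure is 78% power for an odds ratio of 1.55 in a single-covariate GEE at two-sided 0.01.

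On the number of trees, Section 4.2 (Phase 2) refers to "four sun protection decision tree composite models generated in Phase 1", whereas Section 9.0 promises predictive success for three behaviours.

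**The concern.** An EDTM tree is a sequence of if-then rules that ends in a prediction of use or non-use. Testing it means comparing that prediction with what the participant reported. A node size shows how many people follow a path, not whether the path ends in the right prediction. A GEE coefficient shows whether a factor is associated with use on average, not whether the ordered rules classify correctly.

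If Section 11.0 is followed as written, a statement that the trees are valid would rest on analyses that cannot support it, or on a success measure chosen after the data are seen. Section 9.0 names no measure, benchmark or interval. Where most occasions involve use, a percentage correct can look respectable for a rule with no discriminating value.

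**Working it through.** **1. Promise against plan.** Validation needs (a) a tree-predicted use or non-use for each assessment, (b) a cross-classification against reported behaviour, and (c) a named measure with an interval that allows for repeated assessments per person. Section 11.0 contains none of these. The inputs do exist: Section 7.0 records 21 yes/no decision criteria and four behaviours at each assessment.

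**2. The plan's own figure.** The odds ratio is (0.70/0.30)/(0.60/0.40) = 1.556. The power was simulated with 4,000 runs: 60 people × 28 assessments, latent AR(1) correlation 0.10, 70% vs 60% use, 30% of assessments missing, 5% + 5% attrition, robust person-clustered variance, two-sided 0.01. A person-level covariate with dropout spread through each week gives 79.1%, against the stated 78%. Other variants with 28 assessments and the same missingness and correlation give 81.0% to 83.9%. The figure reproduces, but it concerns one coefficient.

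**3. What that effect means for prediction.** Assume the factor is present on half of occasions, and predict use exactly when it is present.
- Overall use = 0.5×0.70 + 0.5×0.60 = 0.65
- Sensitivity = 0.35/0.65 = 53.8%
- Specificity = (0.5×0.40)/0.35 = 57.1%
- Accuracy = 0.35 + 0.20 = 55%
- Always predicting use: accuracy 65%, specificity 0%

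Use exceeds 50% whether or not the factor is present, so this factor alone cannot beat the always-use rule on accuracy. A factor can have the odds ratio the study is powered for and still predict poorly.

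**4. Precision of the missing analysis.** With dropout at week end, completed assessments ≈ 60 × 28 × 0.70 × 0.975 = 1,147, or 19.1 per person. For accuracy of 80% (assumed), half-width = 1.96 × √(0.8 × 0.2 × DE / 1,147), with DE = 1 + 18.1 × ICC.

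For sensitivity and specificity, both assumed 80%, take dropout spread within weeks: 60 × 0.70 × 14 × (0.975 + 0.95 × 0.975) = 1,118 assessments. At 65% use these are 727 use and 391 non-use occasions, and DE uses the per-person counts 727/60 and 391/60. The ICCs are assumed, since the documents give none.

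| ICC | Accuracy ± | Sensitivity ± | Specificity ± |
|---|---|---|---|
| 0 | 2.3 | 2.9 | 4.0 |
| 0.1 | 3.9 | 4.2 | 4.9 |
| 0.3 | 5.9 | 6.1 | 6.5 |
| 0.5 | 7.3 | 7.4 | 7.7 |

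(Half-widths in percentage points.) If correctness followed the plan's AR(1) pattern at 0.10, DE ≈ 1.1/0.9 = 1.22, and the accuracy half-width is about 2.3 × √1.22 ≈ 2.6 points or less, since missed assessments weaken the serial correlation.

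**5. Number of trees.** Three: Section 1.0; Section 4.1; Section 4.2 (generating the decision models); the first aim in Section 9.0; Aim I in Section 11.0. Four: Aim I in Section 2.0; Section 4.2 (Phase 2); Section 7.0 (a model for each assessed behaviour, hats included). Section 9.0 also lists hat use as a primary outcome.

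**The case against.** Several points on the other side have force.

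- **The sensitivity and specificity sentence is background.** It describes EDTM in general, and the study's own commitments name no metric. This stands. However, Section 9.0 ties the promised result to EDTM methodology, and Section 3.0 is where the protocol says what that entails.
- **The analysis may be specified in the cited method texts.** Those texts are not available here. Even so, Section 11.0 assigns the Phase II data to a different analysis and does not refer to them for validation.
- **A reader might infer that Phase II leaves its main question unanswered.** The documents do not support that. The Phase II aim in Section 2.0 concerns theory-driven predictors, which the GEEs address. Validation is promised elsewhere, but it is not in that list of aims, and Section 11.0 calls the study exploratory.
- **A reader might infer that only one-factor GEEs are allowed.** The one-factor model is an example and the covariate count is open. A multi-factor GEE would still not test the ordered tree.
- **A reader might infer that a raw hit rate is planned.** No measure is named, so this is a risk and not a stated plan.
- **The magnitudes rest on assumptions.** This stands. The 60% and 70% rates come from a hypothetical power example, 80% accuracy is assumed, and the larger ICCs far exceed the plan's 0.10. That 0.10 is itself no estimate of clustering: it comes from a table of counts expected under independence (21×21/30 = 14.7, rounded to 15).

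**Conclusion.** The point holds as a gap between promise and plan: the protocol commits to validating each composite tree, and Section 11.0 contains no analysis that would do so. Node sizes and GEE coefficients cannot substitute, whatever the number of covariates. This follows from the text and depends on no numerical assumption.

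The figures show only why the choice of measure matters. A trivial rule reaches 65–70% accuracy at the plan's hypothetical use rates, and treating assessments as independent could understate the half-width on an 80% hit rate by a factor of up to about three (2.3 against 7.3 points at an assumed ICC of 0.5). They also show that the 60 planned participants can support a useful validation. The three-versus-four discrepancy is a real contradiction that leaves the status of the hat-use tree unclear. The change should be made before the Phase II data are analysed.

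**What to change.** In Section 11.0, Aim I, add a validation analysis:

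- Fix the composite trees before Phase II analysis begins.
- For every Phase II assessment, derive each tree's predicted use or non-use from the yes/no criteria. First confirm that the 21 items reproduce every path; the trees and Appendix C are not in the public document.
- State a rule for skipped or unanswered nodes, since Section 4.2 lets participants skip questions and Section 3.0 describes question branching.
- Report sensitivity, specificity and accuracy per behaviour, with 95% confidence intervals that allow for clustering within person, for example a bootstrap that resamples participants.
- Compare accuracy with the majority-class rule for that behaviour.
- Keep node sizes as description only, and remove the inference from node size to importance.

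Reconcile three versus four behaviours in Sections 1.0, 2.0, 4.1, 4.2, 9.0 and 11.0 so that the hat-use tree is validated too. Section 7.0 suggests a likely source to address: the Phase I interviews counted hats as clothing.

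The cost is SAP wording and a little programming, with no new data or participants. The reported success may look less favourable than a raw hit rate would.
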